OVERVIEW Adult men and women will be (50 kg), body mass index grea use of any Cannabis or canna experimental procedures in 15	invited to participate. Inclusion criteria will include iter than 25 kg/m ² , absence of any gastrointestin bis containing products for three days prior to eac adults.	e: age over 18 years, body mass greater than 110 Lbs nal or metabolic diseases, and ability to refrain from ch laboratory visit. The goal is to complete all
Following screening (i.e. med participants will report to the la morning having abstained from instrumented for measurement kept patent via a saline drip.	cal history, and assessment of body composition b on seven separate occasions separated by a n n food for 12-hours, and any products containing t of heart rate and blood pressure. A venous cath	via dual energy X-ray absorptiometry (DEXA)) ninimum of 4-days. Participants will arrive in the CBD for 72-hours. On arrival participants will be heter will be introduced to an arm or hand vein and
Two of the visits will begin wit 30 mg dose of CBD or a place circulating markers of carbohy analysis of blood for circulatin	n measurement of resting metabolic rate followed bo. Postprandial metabolism will be studied usin drate and fat metabolism. Blood will also be sam o markers of liver function	l immediately by ingestion of a liquid meal and a singl ng indirect calorimetry and repeated blood sampling fo npled for determination of CBD pharmacokinetics and

The other five visits will comprise ingestion of different CBD formulations without a meal. Venous blood will be sampled at

C -PROTOCOL	PROTOCOL IRB Form	Protocol # 21-10634H Date Printed: 03/24/2021
Protocol Title: Protocol Status:	Interaction between Cannabidiol, Meal APPROVED	Ingestion, and Liver Function
Date Submitted:	03/03/2021	
Approval Period:	03/24/2021-03/17/2022	
Important Note:	This Print View may not reflect all comment Please check the comments section of the Questions that appear to not have been an for this submission. Please see the system	ts and contingencies for approval. online protocol. swered may not have been required application for more details.
standardized intervals over 4-hours a	and will be analyzed for circulating CBD concentra	tion and markers of liver function.
DETAILS		

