Visit 1: Screening Visit - Duration: ~ During this visit participants will com undergo basic measures of body cor DEXA). Body composition is a know metabolism. DEXA data will be used	0.5 hour plete the Informed Consent, provide a brief medica mposition (height, weight, and waist and hip circum n physiological regulator of CBD concentration, ar d as a statistical co-variable in our final analysis.	al history, and will nference, and nd is related to metabolic rate and postprandial
The remaining seven visits will occur but not the dose, of CBD. The other resting metabolism, ingestion of a m substitution of a placebo for CBD.	r in a random order. Five of these visits will be alm two visits will be almost identical to the other five l eal, measurement of metabolic rate following the n	nost identical, differing only in the preparation, but they will also include measurement of neal, and one of the visits will entail the
Five Visits Not Involving A Test Meal Participants will report to the lab on f having abstained from food for 12-ho for measurement of heart rate and b saline drip.	I ~ 4.5 hours each five separate occasions separated by a minimum o ours, and any products containing CBD for 72-hour lood pressure. A venous catheter will be introduced	of 5-days. Participants will arrive in the morning rs. On arrival participants will be instrumented d to an arm or hand vein and kept patent via a
Following baseline blood sampling (t standardized intervals over 4-hours: concentration. Each blood sample w	time 0), participants will ingest one of the product fo 0, 10, 20, 30, 45, 60, 120, 180, and 240 minutes a ill be ~5 mL.	ormulations. Venous blood will be sampled at and will be analyzed for circulating CBD
In addition, venous blood will also be including alanine aminotransferase (nitrogen. These samples will be take	e sampled and analyzed for circulating factors indic ALT), albumin, alkaline phosphatase, aspartate an en at time 0, 60 and 240 minutes. Each of these b	cative of liver (and also kidney) function, ninotransferase, total bilirubin, and blood urea lood samples will be ~1 mL.
The following formulations will be stu	udied. All products will be standardized to 30mg CE	BD per dose.
1)T-P-S-10 Caliper powder - 30 mg (2)Oil based tincture - 30 mg CBD isc 3)10% CBD Gum Arabic, maltodextr 4)10% CBD Gum Arabic, sorbitol ba 5)CBD Isolate in water	CBD in the form of 300 mg of 10% CBD isolate plate in MCT oil (1:1 ratio of CBD to MCT oil) in base se	

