03/18/2021	NEW FORM Comme Sent (Cvcle 1)	nts		
03/19/2021	NEW FORM Response	ses		
03/23/2021	NEW FORM Responses	ses		
03/24/2021	NEW FORM Comme Received (Cycle 2)	nts		
03/24/2021	NEW FORM Comme Received (Cycle 2)	nts		

Statistical Analysis Plan NCT04971837 04/01/2022

All data, unless otherwise stated, are presented as mean and standard deviation. Statistical analyses were performed using dedicated, commercially available software (SigmaStat for Windows 3.5, Systat Software, Inc., Chicago, IL, USA). Differences in pharmacokinetic parameters between CBD formulations for CBD, and the CBD metabolites were explored using one-way analysis of variance (ANOVA) with repeated measures. Tukey's tests were used to further examine the identified main effects. The thermic effect of food was examined using two-way ANOVA with repeated measures comparing energy expenditure across time for the two conditions (i.e., CBD and placebo); respiratory exchange ratio and circulating concentrations of glucose, insulin, and triglycerides were compared in the same way. The thermic effect of food was also examined by comparing the area under the curve (trapezoidal method). Circulating markers of liver and kidney function were compared across time and between CBD formulations using two-way ANOVA with repeated measures and post-hoc Tukey's tests when appropriate. Relations between circulating CBD concentrations and markers of liver and kidney function. The level of statistical significance was set at p < 0.05.

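### The liver and kidney ANOVA does not use each visit's pre-dose value as a baseline or name the term that answers the formulation question, and this costs power.

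*Combined protocol and SAP*

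**What the plan says.** The SAP (dated 04/01/2022) gives the liver and kidney markers one sentence: "Circulating markers of liver and kidney function were compared across time and between CBD formulations using two-way ANOVA with repeated measures", with "post-hoc Tukey's tests when appropriate". It then sets one general threshold: "The level of statistical significance was set at p < 0.05". It mentions no change from baseline and no pre-dose covariate. It does not say whether the formulation effect, the time effect or their interaction decides the question.

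The protocol (Procedures, Five Visits Not Involving A Test Meal) takes the marker samples "at time 0, 60 and 240 minutes". The same section places time 0 ahead of dosing: "Following baseline blood sampling" comes first and the product is swallowed afterwards. Five formulations are listed, the last being "5)CBD Isolate in water". The overview sets the goal of completing all "experimental procedures in 15" adults. Visits come in random order and are spread over roughly 10 to 12 weeks. The only covariate that the protocol names is DEXA body composition, and the SAP does not repeat it.

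**The concern.** The dose cannot have changed a sample taken before it. If that sample is one of three levels in the ANOVA, one third of each formulation's mean carries no information about the formulation. A participant's marker level can also differ from visit to visit over several weeks. That visit-level part is common to all three samples of the visit, so averaging over them does not remove it.

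The Purpose section makes the acute effect of different formulations on liver markers a stated aim. The phrase about comparing between formulations fits the main effect, and the SAP's pharmacokinetic sentence applies Tukey tests to main effects. If the main effect decides, a null result could be reported as no difference between formulations when the test had little chance of finding one. The value that would remove most of this noise is already collected at every visit.

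**Working it through.** The documents give no SD, target shift or power for these markers, so there is no planned figure to reproduce.

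**Inputs from the documents:** n = 15 participants, 5 fasting formulations, 3 sampling times, alpha 0.05.

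**Assumptions:** within-visit SD se = 1 unit; between-visit SD sv = 0.5, 1 or 2 units; equal variances and sphericity; one formulation shifted by d, the others not. For one shifted formulation out of five, the centred sum of squares is 0.8d², so n × 0.8 = 12.

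**1. Formulation main effect (df 4, 56).** The mean over three times moves by (2/3)d and has error variance sv² + 1/3. The noncentrality is 12 × (2d/3)² / (sv² + 1/3). With d = 1.25:
- sv = 0.5: 8.333 / 0.583 = 14.3, power 84%.
- sv = 1: 8.333 / 1.333 = 6.25, power 45%.
- sv = 2: 8.333 / 4.333 = 1.92, power 16% (15% simulated).

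**2. Formulation-by-time interaction (df 8, 112).** A shift common to all three samples of a visit cancels. The noncentrality is 12 × d² × 2/3 = 12.5 at d = 1.25. Power is 67% at every sv. The main effect falls below the interaction once sv exceeds about 0.7 se.

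**3. Post-dose values adjusted for that visit's time 0.** At a single post-dose time the residual variance is sv² + 1 − sv⁴/(sv² + 1), which is 1.2, 1.5 and 1.8 at sv = 0.5, 1 and 2. Dosing leaves time 0 unchanged, so the full shift d is kept. Two tests at 0.025 each, one at 60 and one at 240 minutes, were simulated.

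**4. Simulated power, uncorrected F tests:**

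| Shift in one formulation | sv | Main effect | Interaction | Adjusted tests |
|---|---|---|---|---|
| 1.25 se at 60 and 240 min | 2 | 15% | 67% | 76% |
| | 1 | 45% | 67% | 85% |
| | 0.5 | 84% | 67% | 94% |
| 1.75 se at 240 min only | 2 | 10% | 95% | 91% |
| | 1 | 23% | 95% | 96% |
| | 0.5 | 50% | 95% | 99% |

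**5. No shift.** Rejection rates stay near 5% for the main effect, the interaction and the pair of adjusted tests, at every sv.

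**6. Shift shared by all five formulations.** For 0.5 se at both post-dose times, the time effect (df 2, 28) has noncentrality 15 × 5 × 0.25 × 2/3 = 12.5 and power 86%. This falls to 50% if participants also differ in their time course with variance 0.25 se². The adjusted formulation tests reject about 5% of the time, which is chance, because they compare formulations only with each other.

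**The case against.** The strongest reply is that the planned two-way ANOVA already contains a sound test. Its formulation-by-time term compares change within visits, so visit-level drift drops out. A reader might infer that drift enters every formulation comparison and that a real shift would easily be missed. The documents do not support that: it is true of the main effect only. For a 240-minute-only shift the interaction matches the adjusted tests, and slightly exceeds them when between-visit variation is large (95% against 91% at sv = 2). At sv = 0.5 the main effect itself has 84% power for the sustained shift.

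A reader might also take drift to mean bias or false positives. Random visit order and error rates near 5% rule that out under these assumptions. Nor does the SAP state that time 0 is an ANOVA level. That is an inference, although no other use of the sample is described.

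Two further replies stand. The variances and shifts are assumed, and one ratio is made to serve six different analytes. Replacing the ANOVA outright would also lose its time effect, while the Purpose section asks whether low-dose CBD affects liver function at all.

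What remains is that the SAP leaves the deciding term open, and that for a sustained shift in one formulation both of its formulation terms have less power than a test that uses the pre-dose value.

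**Conclusion.** The point holds as a loss of efficiency and a gap in specification. The planned analysis is not invalid. The two-thirds dilution and the full between-visit variance in the main effect follow from the design whatever the SDs, provided time 0 is one of the three levels.

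The size of the loss depends on the unknown ratio of between-visit to within-visit SD. For a sustained shift of 1.25 se, moving from the main effect to the adjusted tests gains about 61, 40 and 10 percentage points at ratios of 2, 1 and 0.5. Against the interaction the gain is about 9, 18 and 27 points. For a late-only shift the interaction and the adjusted tests are close. These figures assume 15 completers, equal variances and sphericity. A null main effect alone should not be read as evidence that the formulations have the same effect on liver markers.

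**What to change.** State in the SAP that the formulation main effect over all three times will not be used to judge formulations. Then specify:

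- **Formulation comparison:** analyse the 60- and 240-minute values in a model with participant, formulation and that visit's time-0 value as covariate. Test formulation at each time at 0.025, with Tukey comparisons on the adjusted means.
- **Change common to all formulations:** keep the two-way ANOVA's time effect, 0 against 60 and 240 minutes. The fasting visits have no placebo, so this cannot separate CBD from time of day.
- **Supportive:** report the formulation-by-time interaction.

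The cost is SAP wording, one degree of freedom, a little more analysis, and slightly lower power than the uncorrected interaction for a late-only shift when between-visit variation is large. No new samples are needed. The SAP is written in the past tense, so the data may already have been analysed. If so, the baseline-adjusted analysis should be labelled as added afterwards.
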